### **9.3 sUA Discontinuation Criteria**

Individual Subject sUA Discontinuation Criteria: Subjects with a pre-infusion sUA level  $>6$  mg/dL at 2 consecutive study visits beginning with the Week 2 Visit will discontinue treatment and remain in the study for Follow-Up visits only, including the 30-day Follow-up Email/Phone call, Week 24/End of Study/Early Termination and 3 Month Post-Treatment Follow-up Visits.

Note: The sUA Discontinuation Criteria only pertain to individual subjects and are not sUA Discontinuation Criteria for a group or specific infusion duration.

## 9.4 Selection of Study Population

Subjects diagnosed with gout eligible for this study will have sUA  $\geq 6$  mg/dL and inability to maintain sUA  $< 6$  mg/dL on other urate-lowering therapy or intolerable side effects associated with current urate-lowering therapy, or with a contraindication to xanthine oxidase inhibitor therapy.

### 9.4.1 Inclusion Criteria

Eligible subjects must meet all of the following criteria:

1. Willing and able to give informed consent.
2. Willing and able to comply with the prescribed treatment protocol and evaluations for the duration of the study.
3. Adult men or women  $\geq 18$  years of age.
4. Uncontrolled gout, defined as meeting the following criteria:
  - Hyperuricemia during the screening period defined as sUA  $\geq 6$  mg/dL and;
  - Failure to maintain normalization of sUA with xanthine oxidase inhibitors at the maximum medically appropriate dose, or with intolerable side effects or a contraindication to xanthine oxidase inhibitor therapy based on medical record review or subject interview and;
  - Symptoms of gout including at least 1 of the following:
    - Presence of at least one tophus
    - Recurrent flares defined as 2 or more flares in the past 12 months prior to screening
    - Presence of chronic gouty arthritis
5. Willing to discontinue all oral urate-lowering therapy at least 7 days prior to MTX dosing at Week -4 and remain off of urate lowering therapy when receiving pegloticase infusions during the study.
6. Women of childbearing potential (including those with an onset of menopause  $< 2$  years prior to screening, non-therapy-induced amenorrhea for  $< 12$  months prior to screening, or not surgically sterile [absence of ovaries and/or uterus]) must have negative serum/urine pregnancy tests during Screening:
  - Subjects must agree to use 2 reliable forms of contraception during the study, one of which is recommended to be hormonal, such as an oral contraceptive. Hormonal contraception must be started  $\geq 1$  full cycle prior to Week -4 (start of MTX) and continue for 30 days after the last dose of pegloticase, or at least one ovulatory cycle after the last dose of MTX (whichever is the longest duration after the last dose of pegloticase). Highly effective contraceptive methods (with a failure rate  $< 1\%$  per year), when used consistently and correctly, include implants,

injectables, combined oral contraceptives, some intrauterine devices, sexual abstinence, or vasectomized partner.

7. Men who are not vasectomized must agree to use appropriate contraception so as to not impregnate a female partner of reproductive potential during the study, beginning with the initiation of MTX at Week -4 and continuing through 3-Month Post-Treatment Follow-up.
8. Able to tolerate MTX 15 mg for 4 weeks during the MTX Run-in Period prior to the first dose of pegloticase.

#### **9.4.2 Exclusion Criteria**

Subjects will be ineligible for study participation if they meet **any** of the following criteria:

1. Weight >160 kg (352 pounds) at Screening.
2. Any serious acute bacterial infection, unless treated and completely resolved with antibiotics at least 2 weeks prior to Week -4 Visit.
3. Severe chronic or recurrent bacterial infections, such as recurrent pneumonia or chronic bronchiectasis.
4. Current or chronic treatment with systemic immunosuppressive agents such as MTX, azathioprine, or mycophenolate mofetil; prednisone  $\geq$ 10 mg/day or equivalent dose of other corticosteroid on a chronic basis (defined as 3 months or longer) would also meet exclusion criteria.
5. Known history of any solid organ transplant surgery requiring maintenance Immunosuppressive therapy unless treated and no chronic or active infection confirmed by HBV serology.
6. Known history of hepatitis B virus surface antigen positivity or hepatitis B DNA positivity, unless treated and viral load is negative and no chronic or active infection confirmed by HBV serology.
7. Known history of hepatitis C virus RNA positivity unless treated and viral load is negative.
8. Known history of Human Immunodeficiency Virus (HIV) positivity
9. Glucose-6-phosphate dehydrogenase (G6PD) deficiency (tested at Screening Visit).
10. Severe chronic renal impairment (estimated glomerular filtration rate  $<40$  mL/min/1.73 m^2) at the Screening Visit based on the 4 variable-Modification of Diet in Renal Disease [MDRD] formula or currently on dialysis.
11. Non-compensated congestive heart failure or hospitalization for congestive heart failure or treatment for acute coronary syndrome (myocardial infarction or unstable angina) within 3 months of the Screening Visit, or current uncontrolled arrhythmia, or current uncontrolled BP ( $>160/100$  mmHg) prior to Week -4.
12. Pregnant, planning to become pregnant, breastfeeding, planning to impregnate female partner, or not on an effective form of birth control, as determined by the Investigator.

13. Prior treatment with pegloticase (KRYSTEXXA), another recombinant uricase (rasburicase), or concomitant therapy with a polyethylene glycol-conjugated drug.
14. Known allergy to pegylated products or history of anaphylactic reaction to a recombinant protein or porcine product.
15. Contraindication to methotrexate (MTX) treatment or MTX treatment considered inappropriate.
16. Known intolerance to MTX.
17. Receipt of an investigational drug within 4 weeks or 5 half-lives, whichever is longer, prior to MTX administration at Week - 4, or plans to take an investigational drug during the study.
18. Liver transaminase levels (AST or ALT) > upper limit of normal (ULN) or albumin < the lower limit of normal (LLN) at the Screening Visit.
19. Chronic Liver Disease.
20. White blood cell count < 4,000/uL, hematocrit < 32 percent, or platelet count < 75,000/uL.
21. Currently receiving systemic or radiologic treatment for ongoing cancer.
22. History of malignancy within 5 years other than non-melanoma skin cancer or in situ carcinoma of cervix.
23. Uncontrolled hyperglycemia with a plasma glucose value >240 mg/dL at Screening that is not subsequently controlled by the end of the Screening.
24. Diagnosis of osteomyelitis.
25. Known history of hypoxanthine-guanine phosphoribosyl-transferase deficiency, such as Lesch-Nyhan and Kelley-Seegmiller syndrome.
26. Unsuitable candidate for the study, based on the opinion of the Investigator (e.g., cognitive impairment), such that participation might create undue risk to the subject or interfere with the subject's ability to comply with the protocol requirements or complete the study.
27. Alcohol use in excess of 3 alcoholic beverages per week.
28. A known intolerance to all protocol standard gout flare prophylaxis regimen (i.e. colchicine and/or non-steroidal anti-inflammatory drugs and/or low-dose prednisone  $\leq$  10 mg/day).
29. Currently receiving urate-lowering therapies and unable to discontinue treatment at least 7 days prior to MTX dosing at Week -4 and remain off of urate lowering therapy when receiving pegloticase infusions during the study.
30. Current pulmonary fibrosis, bronchiectasis or interstitial pneumonitis. If deemed necessary by the Investigator, a chest X-ray may be performed during Screening

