#### **Restricted Medications**

Subjects will be directed to discontinue current urate-lowering therapy prior to screening. Other medications used at the time of study initiation may be continued at the discretion of the Investigator.

The following medications are prohibited during the study:

- Concomitant therapy with allopurinol, febuxostat or other urate lowering medications or a polyethylene glycol-conjugated drug
- Systemic or radiologic treatment for ongoing cancer, excluding non-melanoma skin cancer
- Current or chronic treatment with systemic Immunosuppressive agents

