### **9.5.10 Restricted Medications**

Subjects should not receive the following medications from the time of Screening through the end of pegloticase and MTX treatment:

- Oral urate-lowering therapies including allopurinol, febuxostat, probenecid, lesinurad, or other ULT for gout; re-introduction of oral ULTs should not start until after the End of Pegloticase Visit (or End of Study) laboratory tests are collected.
- Any PEG-conjugated drug
- Any other investigational agent
- Methotrexate (other than study investigational product), azathioprine, mycophenolate mofetil, or other systemic immunosuppressants aside from glucocorticoids for gout flare prophylaxis (< 10 mg prednisone or equivalent per day) or intermittent gout flare treatment
- If a subject is treated with antibiotics, refer to Section 9.5.7.3.2.2.
- Systemic immunosuppressive agents

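### Exclusion 5 (solid organ transplant) carries an exception about hepatitis B serology that fits only exclusion 6, leaving a narrow gap for recipients maintained on a low corticosteroid dose alone

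*Protocol*

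**What the plan says.** Five parts of the protocol bear on this point.

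- **Exclusion 5** (synopsis and section 9.4.2, same wording): "Known history of any solid organ transplant surgery requiring maintenance Immunosuppressive therapy unless treated and no chronic or active infection confirmed by HBV serology".
- **Exclusion 6**, on hepatitis B surface antigen or DNA positivity, has the exception "unless treated and viral load is negative and no chronic or active infection confirmed by HBV serology".
- **Exclusion 4**: "Current or chronic treatment with systemic immunosuppressive agents such as MTX, azathioprine, or mycophenolate mofetil". A second limb covers chronic prednisone at 10 mg/day or more, or an "equivalent dose of other corticosteroid on a chronic basis (defined as 3 months or longer) would also meet exclusion criteria".
- **The rule for the list**: "Subjects will be ineligible for study participation if they meet" any one of the criteria.
- **Restricted medications**: section 9.5.10 bars, from Screening to the end of pegloticase and MTX treatment, "Methotrexate (other than study investigational product), azathioprine, mycophenolate mofetil, or other systemic immunosuppressants aside from glucocorticoids for gout flare prophylaxis" (below 10 mg prednisone or equivalent per day) or for intermittent flare treatment. It then lists systemic immunosuppressive agents again without qualification. The synopsis list prohibits "Current or chronic treatment with systemic Immunosuppressive agents".

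The summary of changes for Version 5.0 does not mention exclusion 5.

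**The concern.** An exception in an exclusion criterion should describe a state in which the reason for the exclusion no longer applies. Here it does not. In a transplant criterion there is no infection to be treated or cleared, and hepatitis B status does not decide whether a graft needs maintenance immunosuppression. A site applying exclusion 5 as printed must work out what the recipient has to have been treated for, and would release someone on the strength of a result unrelated to the transplant.

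What is at stake is eligibility and safety rather than estimation. Every subject receives methotrexate, and section 7.1.4 lists greater susceptibility to infection among its risks. The transplant criterion presumably exists to keep long-term immunosuppressed patients out of that setting. If its exception empties it for some of them, the decision falls to other criteria that were not written for transplant recipients.

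**Working it through.** No arithmetic applies: the point depends on no rate, sample size or error level. The check sets the criteria side by side and follows a recipient through them.

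**Step 1. Is the clause really in exclusion 5?** Yes. The synopsis and section 9.4.2 carry it identically, which makes a fault in reading the PDF unlikely.

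**Step 2. Where does the clause fit?** Exclusion 6 has three conditions: treated, viral load negative, and no chronic or active infection on HBV serology. Exclusion 5 has the first and third, without the viral-load condition. Both refer to a viral infection, which is the subject of exclusion 6 and not of exclusion 5.

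**Step 3. What does exclusion 5 release?** Only a recipient who meets both conditions: treated (whatever that means here), and absence of infection confirmed by serology. A recipient without the confirming result stays excluded. Neither the Schedule of Assessments nor the safety laboratory list in section 9.6.1.8 includes HBV serology, so the result would have to come from outside the scheduled tests.

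**Step 4. What do the other criteria do with a released recipient?**

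| Maintenance regimen, with exclusion 5 lifted | Exclusion 4 | Section 9.5.10 |
|---|---|---|
| Azathioprine, mycophenolate mofetil or another systemic immunosuppressant | Excluded | Barred |
| Chronic prednisone 10 mg/day or more, or equivalent | Excluded | Outside the carve-out |
| Corticosteroid alone, below that level | Not clearly caught | Not clearly permitted |

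The first two rows are ineligible through exclusion 4, whatever exclusion 5 says.

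**Step 5. The third row.** Exclusion 4 names a corticosteroid threshold, and a dose below it falls outside that limb. One could argue that a low-dose corticosteroid still counts as a systemic immunosuppressive agent under the first limb, but an explicit threshold would then serve little purpose. Section 9.5.10 decides by indication as well as dose: its carve-out is for glucocorticoids given for gout flare prophylaxis or intermittent flare treatment. Maintenance of a graft is neither. Such a recipient could therefore pass the numbered exclusions on the day of screening while taking a therapy that the on-study list does not clearly allow.

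**The case against.** The strongest reply is that this is an editorial slip with almost no operational effect. Most of that stands. It disposes of four stronger readings that a reader might draw from the wording.

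- **That recipients on maintenance immunosuppression may enrol.** They may not, in general. The exception lifts exclusion 5 only, and exclusion 4 has no transplant or HBV exception.
- **That exclusions 4 and 5 contradict each other.** Failing to meet one exclusion does not make a person eligible, so both can be applied together. The defect is a criterion that makes no sense as worded, not two rules that cannot both hold.
- **That exclusion 5 is the only safeguard for the low-dose corticosteroid case.** Section 9.5.10 does not clearly permit that therapy. Exclusion 15 (MTX contraindicated or considered inappropriate) and exclusion 26 (unsuitable in the investigator's opinion) also give the site grounds to refuse.
- **That the gap could decide the primary result.** SAP section 3.4.1 requires an upper 95% Clopper-Pearson limit below 13%. With 110 subjects, 7 events give 12.67% and 8 give 13.83%, so one subject can matter arithmetically. The documents give no frequency for this kind of recipient and no reason to expect a different infusion-reaction risk. Low-dose prednisone is a permitted flare prophylaxis for all subjects, every subject receives a corticosteroid before each infusion, and the protocol attributes antibody reduction to MTX.

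It is also fair to say that copying from exclusion 6 is an inference, since the documents do not state it. What the reply does not remove is that an operative eligibility rule, printed twice, contains a condition with nothing to refer to. Investigator discretion and an on-study medication list are not substitutes for a clear entry criterion.

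**Conclusion.** The point holds as a wording defect with a narrow consequence. Exclusion 5 itself does not exclude a treated transplant recipient with confirming HBV serology. Exclusion 4 excludes those on systemic immunosuppressants or on chronic prednisone at or above its threshold. It does not clearly catch a recipient maintained on a lower corticosteroid dose alone, and for that person the exclusion list and section 9.5.10 do not give sites one clear answer.

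Few if any subjects are likely to be affected. They would need a transplant, uncontrolled gout, maintenance on a low corticosteroid dose alone and a serology result that the study does not schedule, and would also have to meet the renal and liver criteria. The documents allow no estimate of the number. The sample size, the success rule and the planned analysis are unaffected.

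The conclusion assumes that the treated condition is taken as met, and that a corticosteroid below the exclusion 4 threshold is not in itself a systemic immunosuppressive agent under that criterion's first limb. If the sponsor defines it as one, the gap closes, but exclusion 5 still needs correcting.

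**What to change.** Reconcile exclusions 4, 5 and 6 with the restricted-medication lists in the synopsis and section 9.5.10, so that the status of a transplant recipient is stated once and agrees everywhere. Unless the sponsor confirms that an HBV-based exception for transplant recipients was intended, remove the exception from exclusion 5 in both the synopsis and section 9.4.2, and keep it in exclusion 6. If it was intended, the protocol should say what treated means in exclusion 5 and where the serology result is to come from. Whether corticosteroid maintenance below the exclusion 4 threshold is allowed is for the sponsor to state; this review does not propose a rule.

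The cost is one clause in two places plus a consistency check, in an amendment or a clarification to sites. It adds no test, visit or analysis.

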### **9.4.3 Removal of Subjects from Therapy or Study**

Every effort should be made to retain a subject in the study to monitor their safety for at least 3-months of follow-up. Subjects who are removed from pegloticase therapy should remain on study for Follow-Up visits only, including the 30-day Follow-up Email/Phone call, Week 24/End of Study/Early Termination and 3 Month Post-Treatment Follow-up Visits barring withdrawal of consent for study participation. However, subjects may withdraw consent or discontinue participation from the study at any time, without prejudice to further treatment. In addition, the Investigator may discontinue a subject from treatment at any time. The primary reason for discontinuation from the study and/or study drug should be recorded on the eCRF.

#### **9.4.3.1 Removal of Subjects from Pegloticase Therapy**

For subjects who do not complete therapy through Week 24, the reason for discontinuation from the therapy should be recorded on the eCRF using 1 of the following categories:

- Lack of Efficacy. (i.e., sUA level  $>6$  mg/dL at 2 consecutive study visits beginning with the Week 2 Visit).
- Adverse Event. The subject experiences an AE that imposes an unacceptable risk to the subject's health (e.g., anaphylactic reaction), or the subject is unwilling to continue therapy because of an AE. Subjects who discontinue treatment due to an AE should be followed until resolution or stabilization of the AE, or an adequate explanation for the event is obtained.
- Physician Decision. The Investigator has determined that pegloticase administration poses an unacceptable risk to the subject (specify reason).
- Withdrawal of Consent. Subject refusal of additional therapy (specify reason).
- Lost to Follow-up. The subject does not return to the clinic for scheduled assessments and does not respond to the site's attempts to contact the subject.
- Study Terminated by Sponsor. The Sponsor, IRB, or regulatory agency terminates the study.
- Pregnancy
- Death

##### **9.4.3.1.1 Study considerations for subjects ending pegloticase infusions prior to 24 weeks**

- Methotrexate, along with folic acid, will be discontinued at the time of cessation of pegloticase infusions prior to Week 24.
- All subjects will complete the End of Pegloticase Infusions Visit and should be encouraged to remain on study and attend all Follow-Up visits, including the 30-day Follow-up Email/Phone call, Week 24/End of Study/Early Termination and 3 Month Post-Treatment Follow-up Visits barring withdrawal of consent from study participation.
- Activities related to pre/post infusion monitoring or medication dispensation will not be completed once a subject has stopped pegloticase infusions. These activities include:
  - MTX compliance/reconciliation

- IR prophylaxis
- IR prophylaxis compliance
- Folic acid compliance
- Pegloticase infusion
- Pegloticase PK sampling
- Pre-infusion MTX Polyglutamate sampling
- MTX drug/dispensation related items

Post-Treatment Follow-up:

The intent is to obtain at least 3 months of follow up on each subject after cessation of pegloticase infusions. If the subject ends treatment early but remains in the study and the 3-month Post-Treatment Follow-up Visit occurs prior to Week 24, the 3-month Post-Treatment Follow-up Visit will be adjusted accordingly based on the timing of the last treatment.

#### **9.4.3.2 Removal of Subjects From Study**

In addition to completion of therapy, the Follow-Up visits, the Week 24 visit and the reason for discontinuation from the study should be recorded on the eCRF using one of the following categories:

- Lost to Follow-up. The subject does not return to the clinic for scheduled assessments and does not respond to the site's attempts to contact the subject.
- Withdrawal of Consent. The subject withdraws from the study. The clinical site should attempt to determine the underlying reason for the withdrawal and document it on the eCRF; (i.e. AE, voluntary withdraw), Specify.
- Study Terminated by Sponsor. The Sponsor, IRB, or regulatory agency terminates the study.
- Death.

If a subject is lost to follow-up, every reasonable effort should be made by the study site personnel to contact the subject. At least two phone calls and a registered letter should be documented before considering subject lost to follow-up. When a subject withdraws before completing the study, attempts of follow-up information should be documented in the source documents to include reasons of withdrawal.

#### **9.4.4 Replacement Policy**

##### **9.4.4.1 Subjects**

In general, subjects that prematurely discontinue from the study for any reason will not be replaced. An exception may be made for subjects who are unevaluable due to the impact of the COVID-19 pandemic and associated restrictions on movement and work. Subjects unable to receive treatment or be evaluated due to restrictions during the COVID-19 pandemic may be replaced, at the discretion of the sponsor. This may result in more subjects than originally planned being enrolled into the study to allow for the originally planned number to be evaluable for the primary efficacy analysis.

#### **9.4.4.2 Centers**

A center may be closed and/or replaced for several reasons. Prior to a site being recommended for closure, the site PI, Medical Monitor, Study Manager and possibly the Site Monitor will discuss the decision for closure.

#### **9.4.4.3 Screen Failures**

Subjects who do not meet all of the inclusion criteria or meet any of the exclusion criteria will be considered screen failures. In addition, subjects who are unable to tolerate MTX at an oral dose of 15 mg weekly during the MTX Run-in Period will be considered screen failures. Screen failure subjects who are females of childbearing potential who took at least one dose of MTX, will receive a Safety Follow-up Phone call/E-mail approximately 30 days after the last dose of MTX to verify at least one ovulatory cycle after the last dose of MTX. If the subject has not ovulated, a urine pregnancy test will be performed at the study site. Screen failure subjects who receive at least 1 dose of MTX and are non-vasectomized males will receive a Phone/E-mail/Site Visit 3 months after MTX discontinuation regarding partner pregnancy.

Screen failure subjects may be allowed to rescreen for the study if both the Investigator and Sponsor are in agreement regarding rescreening and if the Investigator determines that the subject can satisfy all of the eligibility criteria.

